### 3 Outcomes, Exposures, and Additional Variables of Interest

#### 3.1 Primary Outcome(s)

- The primary outcome is PHQ-9 at 1-month post-randomization (T2).

#### 3.2 Secondary Outcome(s)

- PHQ-9 at 3-months post-randomization (T3).
- GAD-7 at 1 and 3 months post-randomization
- PHQ-10 at 1 and 3 months post randomization
- PTSS at 1 and 3 months post randomization
- Quality of life: visual analog scale at 1 and 3 months post randomization

#### 3.3 Other outcomes

- Mindfulness Attention Awareness Scale (MAAS) at 1 and 3 months post randomization

#### 3.4 Other variables of interest.

- Feasibility, acceptability, usability, and participant feedback gathered through semi-structured interviews.

#### 3.5 Primary predictors

The primary predictors are the three intervention components listed in table 3. Detailed descriptions of these components are provided in the protocol paper.

Table 3		
Intervention component	Default Level	Comparator Level
Dose	Low dose	High dose
Non-responders	App-based	Therapist-based
Initiation	App-based	Therapist-based

### 4 Statistical Analysis Plan

The main goal of these intention-to-treat analyses is to estimate main effects and interactions of combined experimental conditions to be able to determine which LIFT use case is best, i.e., should any of the factors should move from the “low” to the “high” levels (**Table 1**). Our overall analytic approach will be guided by frameworks presented by Collins and Collins & Kugler. To understand general patterns in the data, we will first calculate raw means, medians, and measures of variability at each time point for the primary and secondary outcomes. These will be grouped by the main effect of each factor (e.g. standard vs high-dose), collapsed over the other factors. We will also examine these descriptive statistics by groups as defined by the two-way and three-way interactions of the factors.

The primary quantitative outcome is the PHQ-9. The primary time point of interest is 1-month post-randomization (T2). We will estimate the main effects of each intervention component on the primary outcome and of all pairwise interactions of those components at each follow-up time point using a general linear model with unstructured covariance to take into account repeated measures on individuals over time. To estimate effects of each intervention component on PHQ-9, the model will include as outcomes PHQ-9 score at baseline (T1) and each follow-up time point (T2, T3). The model will include fixed effects for: time point (T2 and T3), the time-by-component and time-by-pairwise up to five-way interactions, and the variables used in the minimization allocation algorithm. We do not include the effects of the components at

baseline in the statistical model. This constrains the baseline comparisons to be equal, which is appropriate in a randomized trial and increases power. The model will allow us to estimate PHQ-9 change at the primary time point of interest (T2) and the final follow-up time point (T3). The constrained longitudinal model is parameterized below.

$$Y_{ij} = \beta_0 + \beta_1 c1_{ij} T_{ij} + \beta_2 c2_{ij} * T_{ij} + \beta_3 c3 * T_{ij} + \beta_4 c1c2 * T_{ij} + \beta_5 c1c3 * T_{ij} + \beta_6 c2c3 * T_{ij} + \beta_7 c1c2c3 * T_{ij} + \beta_8 * T_{ij} + \epsilon_{ij}, \\ \epsilon_{ij} \sim N(0, \Sigma_{ij}),$$

where  $c1, c2, c3$  are the intervention components (effect coded) assigned to person  $i$  at time  $j$  ( $i = 1, \dots, n; j = 0, 1, 2$ ),  $Y_{ij}$  is the outcome for participant  $i$  at time  $j$ ,  $T_{ij}$  is the indicator of person  $i$  at time point  $j$  (with T1 coded as 0). Note that in this model we assume time 0 is the reference for the  $T_{ij}$  variable, and hence the effects of the intervention components are assumed to be 0 at time 0.  $\Sigma_{ij}$  is the residual correlation matrix, which we will assume to be unstructured, to take into account correlation within individuals across time. Example SAS code for fitting this model is shown in **Appendix A**. Note also that in practice we will adjust for the variables upon which the allocation was minimized. However, when PHQ-9 is the outcome, we will not adjust for baseline PHQ-9, and similarly for PHQ-10.

After examining the model, we will assemble a multicomponent intervention package. In our original protocol paper, we powered based on a 2-unit main effect, but because of increase in power due to an increase in sample size, we lowered the threshold to 1.6 units. If a component has a main effect on PHQ-9 at T2 of  $\geq 1.6$  units or a p-value  $< 0.05$ , and no clinically significant interaction (i.e., achieving the benchmark) with another component, then the superior level of the component will be retained for the intervention package. Otherwise, if there is no clinically significant main effect or interaction (differences less than the benchmark of 1.6 units or p-value  $> 0.05$ ), the default (reference) level of the component will be retained. We will reconsider inclusions based on the presence of large (effect  $\geq 1.6$  units or p-value  $< 0.05$ ) interactions. This decision making is based on the approach outlined in Collins et al.

Although the secondary time point (T3) will not be used in the *primary* decision-making process, we may reconsider our inclusions (i.e., combinations of high and low levels) if there is a large change in effect between T2 and T3. We will then examine secondary outcomes, as well as feasibility and acceptability metrics, as a next step in the decision-making process. We may reconsider our inclusions if there is a large effect in the opposite direction from the primary model, or if feasibility and acceptability metrics, for example, indicate that the “high” level of the component is not acceptable to participants.

Given the factorial design, we will use effect coding, rather than dummy coding, for analyzing the effects of the intervention components. If the sample size is equal per condition, all of the tests of main effects and interactions are uncorrelated—that is, the main effect of a condition is the same even if other treatment conditions and interactions are included in the statistical model. Even with unequal sample sizes across conditions (as may occur with differential dropout by condition), if the imbalance is minor, the correlations between effects should be small.

Missing outcome data due to dropout or missing intermediate visits is expected to be at most 20%. Because the model will be fit using a full maximum likelihood method, we will be able to account for predictors of missingness in the model in order to obtain valid estimates of the main component effects, thanks to the property that the response can be missing at random (MAR) as defined by Little and Rubin. In practice, we will compare baseline characteristics of completers and non-completers. If we find that any covariates predict missingness, we will adjust for these variables in the model as a sensitivity analysis.

# 6 Appendices

## 6.1 Appendix A

**SAS code for fitting the general linear model with unstructured covariance and constrained so that baseline is equal.**

```
PROC MIXED DATA=analysis METHOD=REML CL noclprint=10;
  title "cLDA model";
  CLASS recordid time mz_icu mz_age /*mz_phq9*/ mz_phq10 mz_site;
  model phq9total =
    t2 t3
    /* regression coefficients at 1-month post-intervention */
    t2*dose t2*symp t2*call t2*dose*symp t2*dose*call t2*symp*call t2*dose*symp*call
    /* regression coefficients at 3-month post-intervention */
    t3*dose t3*symp t3*call t3*dose*symp t3*dose*call t3*symp*call t3*dose*symp*call
    mz_icu mz_age /*mz_phq9*/ mz_phq10 mz_site / solution;
    /* 1-month post-intervention effects (2*regression coefficient) */
    * MAIN EFFECTS;
    estimate "dose main effect t2"      dose*t2 2;
    estimate "symptom main effect t2"    symp*t2 2;
    estimate "call main effect t2"      call*t2 2;
    * TWO-WAY INTERACTIONS;
    estimate "dose, symptom interaction effect t2"      dose*symp*t2 2;
    estimate "dose, call interaction effect t2"      dose*call*t2 2;
    estimate "symptom, call interaction effect t2"      symp*call*t2 2;
    * THREE-WAY INTERACTION;
    estimate "dose, symptom, call interaction effect t2" dose*symp*call*t2 2;
    /* 3-month post-intervention effects (2*regression coefficient) */
    * MAIN EFFECTS;
    estimate "dose main effect t3"      dose*t3 2;
    estimate "symptom main effect t3"    symp*t3 2;
    estimate "call main effect t3"      call*t3 2;
    * TWO-WAY INTERACTIONS;
    estimate "dose, symptom interaction effect t3"      dose*symp*t3 2;
    estimate "dose, call interaction effect t3"      dose*call*t3 2;
    estimate "symptom, call interaction effect t3"      symp*call*t3 2;
    * THREE-WAY INTERACTION;
    estimate "dose, symptom, call interaction effect t3" dose*symp*call*t3 2;
    REPEATED time / TYPE=un SUBJECT=recordid R RCORR;
RUN;
```

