For aims 1, 3 and 4 each participant will be asked to complete a singular study visit that will last approximately 30-60 minutes. During this study visit, post consent, the individual may be asked to do the following:

- Find and install the Pattern Health app (aim 1 and aim 4)
- Register to the LIFT2 study (aim 1 and aim 4)
- Complete baseline survey (aim 1 and aim 4)
- Randomize to 1 of 3 groups or screen fail purposely (aim 1 and aim 4)
- Audio-recording for interview using qualitative analyses (aim 3)
- Provide feedback on app content and usability (aim 1, 3, and 4)

For aim 2, each consented patient will be asked to complete up to four individual study visits.

- **Baseline:** this visit is to occur post-consent (same day, ideally) at the time of hospital admission just prior to discharge. However, this visit may occur at the time of hospital discharge within 7 days of returning to home. At this visit, the following will occur:
 - App Registration
 - Baseline Survey Completion
- **T1 (Day 0) (+30 days):** this visit is to occur at the time of hospital discharge to home, ideally within the first week (7 days) of returning to home; however, it can occur up to 1 month (30 days) from the time of hospital discharge to home. At this visit, the patient will complete the T1 survey via the app, which includes the PHQ-9, PTSS, PHQ-10, and MAAS surveys. Score dependent, the patient will be randomized to 1 of 8 intervention combinations. If the patient's psychological distress score is too low; he/she will receive an automated alert via the app describing they are not eligible and their study participation is complete.
- **T2 (Day 30) (+60 days):** this visit is to occur post 1 month randomization for those patients who remain eligible to participate in the study. PHQ-9, PTSS, PHQ-10, and MAAS surveys will be administered again. If the patient's survey scores indicate high levels of distress, as defined by a triggered SI alert or increased distress score from T1, a delegated study team member will contact the patient for safety precautions.
- **T3 (Day 90) (+30 days):** this visit is to occur post 3 months randomization for those patients who remain eligible to participate in the study. PHQ-9, PTSS, PHQ-10, and MAAS surveys will

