**Activity Log**

January 08, 2020 – [name] moved the SAP to this newly formatted file.

January 31, 2020 – Added table of statistical power; weaved in some of the text from the protocol paper

---

---

into the statistical analysis section. Added parameterization of the model and example SAS code.

July 20, 2022 – Added more information on sample size.

Now computing power for a range of effect sizes given 240 participants with 20% dropout (i.e., 192 participants after dropout).

August 5, 2022 – Adding section about minimization; adding notes about determining a threshold

June 23, 2023 – Clarifying that decisions will be made both in relation to effect size and p-value

June 29, 2023 – Updated data decisions regarding windows

August 22, 2023 – Updates to note that when PHQ-9 is the outcome, we do not adjust for PHQ-9 stratified; similarly for PHQ-10.

November 28, 2023 – Error fixed in power calculation simulation code. (Accidentally powered on T3 main effect due to confusion about naming of time points.)

---

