## 2.4 Randomization

The combination of the three factors each at two levels results in 8 experimental conditions. Allocation of the patients into one of the 8 experimental conditions (240 patients randomized with 30 in each condition) occurs at the time of T1 data collection completion (i.e., the first data collection after arrival home from the hospital). To ensure balance between the conditions on these important confounders, allocation is stratified by site (Duke, Colorado, Washington/Oregon), medical vs. surgical ICU vs. not applicable, depression symptom score at T1 (PHQ-9 < 15,  $\geq 15$ ), physical symptom score at T1 (PHQ-10 < 10,  $\geq 10$ ), and age (< 50,  $\geq 50$ ). Because of the large number of stratification variables relative to the experimental condition size, treatment assignment is conducted via a dynamic allocation minimization method. This algorithm is programmed directly within the LIFT mobile app platform.

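### The primary model adjusts for age and T1 PHQ-10 only through two-level cuts; adding the measured values would gain a little precision at almost no cost

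*SAP*

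**What the plan says.** SAP Section 2.4 (Randomization) lists the minimisation variables: site, ICU type, T1 PHQ-9 (cut at 15), T1 PHQ-10 ("physical symptom score at T1 (PHQ-10 < 10" against 10 or more) and age (under 50 against 50 or over).

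SAP Section 4 carries these into the analysis: "Note also that in practice we will adjust for the variables upon which the allocation was minimized". It does not say in what form. Appendix A does: "CLASS recordid time mz_icu mz_age /*mz_phq9*/ mz_phq10 mz_site". The model line then closes with "mz_icu mz_age /*mz_phq9*/ mz_phq10 mz_site / solution", so each covariate is a category with a single coefficient across T1, T2 and T3.

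PHQ-9 is handled differently. Its T1 score stays in the model as a measured value, since "the model will include as outcomes PHQ-9 score at baseline (T1) and each follow-up time point (T2, T3". Its category is commented out, in line with the Activity Log: "when PHQ-9 is the outcome, we do not adjust for PHQ-9 stratified; similarly for PHQ-10".

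The measured PHQ-10 score exists for everyone who is randomised. Protocol Section 7 (Study Visits) says that at T1 "the patient will complete the T1 survey via the app, which includes the PHQ-9, PTSS, PHQ-10, and MAAS surveys", and SAP Section 3.2 analyses the same scale as a secondary outcome ("PHQ-10 at 1 and 3 months post randomization"). That exact age is held is an inference from the age cut, the adult eligibility criterion and the demographic items in the baseline survey (Protocol Appendix 1, note b). Neither document plans to use age or T1 PHQ-10 as a continuous covariate.

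**The concern.** The allocation algorithm needs categories; the analysis model does not. If a covariate relates to the outcome roughly linearly, a two-level cut recovers only part of what the measured value would explain, and the rest stays in the residual variance.

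There is room for other T1 measures to help. In the SAP's covariance matrix, T1 PHQ-9 explains only 17% of the variance of T2 PHQ-9. Power at the 1.6-point benchmark sits at the 80% target with no margin. All seven T2 effects share the same residual variance, and the decision rule in SAP Sections 1.1 and 4 uses p < 0.05 as one of its criteria. What is at stake is a small amount of precision, available from data already collected.

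**Working it through.** **Inputs from the SAP.** Var(T1) = 27.95, Var(T2) = 19.28 and Cov(T1,T2) = 9.67 (Appendix B); 192 participants at T2, 96 per factor level (Table 2); benchmark 1.6 points (Section 2.3); alpha 0.05, two-sided.

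**Inputs not in the documents, so assumed.** The correlations of T1 PHQ-10 with PHQ-9 at T1, T2 and T3; a roughly normal covariate with a linear effect; a share on either side of the cut between 50/50 and 75/25.

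**1. The plan's own figure.**
- T1–T2 correlation ρ = 9.67/√(27.95 × 19.28) = 0.417; squared, 0.17.
- Var(T2 given T1) = 19.28 − 9.67²/27.95 = 15.93.
- SE of an effect = 2 × √(15.93/192) = 0.576.
- Power at 1.6 points = Φ(1.6/0.576 − 1.96) = 79.3%, against 79.8% in Table 2, which came from 500 simulated datasets. The figure reproduces without any covariate.

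**2. What a cut keeps.** For a normal covariate cut at proportion p, the share of its explained variance that is kept is k = φ(z)²/(p(1−p)). This is 0.64 at 50/50 and 0.54 at 75/25. The correlation of the cut with any outcome is r√k.

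**3. Effect on the T2 standard error.** T1 PHQ-9 is already in the model, so only what PHQ-10 adds beyond it counts. With r1 and r2 the covariate's correlations with PHQ-9 at T1 and T2, the partial correlation is (r2 − r1ρ)/√((1 − r1²)(1 − ρ²)), and SE = 0.576 × √(1 − partial r²).

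Example with r1 = 0.5 and r2 = 0.4:
- Score: (0.4 − 0.5 × 0.417)/√(0.75 × 0.826) = 0.244; squared, 0.059; SE = 0.559.
- Cut at 50/50 (√k = 0.798, so 0.399 and 0.319): (0.319 − 0.399 × 0.417)/√(0.841 × 0.826) = 0.18; squared, 0.034; SE = 0.566.
- The score narrows the SE by about 1.3%.

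**4. Range.** The table fits Appendix A's own form (one coefficient across all times) by generalised least squares to the SAP matrix plus the assumed correlations. Ranges run from a 50/50 to a 75/25 cut.

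| Assumed correlation of T1 PHQ-10 with PHQ-9 at T1/T2/T3 | Share of remaining T2 variance | SE with cut | SE with score | SE narrower by | Power gain at 1.6 (points) |
|---|---|---|---|---|---|
| 0.5/0.3/0.2 | 1.4% | 0.5753–0.5755 | 0.5746 | about 0.1% | about 0.1 |
| 0.6/0.4/0.3 | 4.3% | 0.571–0.572 | 0.566 | 0.9–1.1% | 0.7–0.9 |
| 0.5/0.4/0.3 | 5.9% | 0.566–0.568 | 0.559 | 1.3–1.6% | 1.0–1.3 |
| 0.5/0.5/0.4 | 13.7% | 0.554–0.558 | 0.537 | 3.2–3.9% | 2.3–2.9 |

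The last row requires T1 PHQ-10 to correlate 0.5 with T2 PHQ-9, more than T1 PHQ-9 itself does (0.417). It is an outer case.

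**5. In points.** In the third row, the smallest estimate that reaches p < 0.05 moves from 1.96 × 0.568 = 1.11 (75/25 cut) to 1.96 × 0.559 = 1.10.

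**6. Separate T2 and T3 coefficients.** Letting the score's coefficient differ by time point takes the SE from 0.5746 to 0.572 in the first row, from 0.566 to 0.564 in the second and from 0.537 to 0.535 in the last. It leaves the third row unchanged.

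**The case against.** The strongest reply is that adjusting for minimisation factors in the form used for allocation is a standard, valid choice that respects the design. Chance imbalance within a category is already reflected in the standard error. All of this stands. The model also holds T1 PHQ-9 undichotomised, so most of what a correlated symptom score could add is already there. That stands too, and it is why the gain is small.

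Three stronger readings are tempting, and the documents do not support them:

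- A reader might infer that dichotomising throws away 36% to 46% of the information. That is a share of whatever the covariate explains, not of the trial's precision. It also assumes normality, linearity and a cut between 50/50 and 75/25. A uniform covariate loses 25% at the median; a normal one loses 51% at 80/20. The documents give no distribution for either variable.
- A reader might infer that the stated power is overstated. The simulation in Appendix B has no covariates, and its figure reproduces. Adjusting for a prognostic category would be expected to add to that power rather than reduce it.
- A reader might infer that coarse covariates undermine the missing-at-random argument. No calculation shows this. T1 PHQ-9 carries information on dropout through the likelihood, and SAP Section 4 already plans a sensitivity analysis that adjusts for covariates found to predict missingness.

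**Conclusion.** The point holds as a modest, optional gain in efficiency. The primary model uses age and T1 PHQ-10 only as two-level factors although the measured values are, or evidently are, available. No bias follows, the analysis is valid and the 79.8% power stands.

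If T1 PHQ-10 explains 1% to 6% of the T2 PHQ-9 variance left after T1 PHQ-9, the score narrows the T2 standard error by about 0.1% to 1.5%, or about 0.1 to 1.3 points of power at 1.6 points. A gain of 3% to 4% would need PHQ-10 to predict later PHQ-9 better than PHQ-9 does. These figures rest on assumed correlations, a roughly normal score and a linear effect. The gain from age is not quantified, because the documents give nothing to base it on.

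**What to change.** In SAP Section 4 and Appendix A, pre-specify measured age and the T1 PHQ-10 total score as continuous covariates in addition to mz_age and mz_phq10. Keep mz_icu and mz_site as categories. When PHQ-10 is the outcome, omit the T1 PHQ-10 covariates, as the SAP already intends, and use the T1 PHQ-9 score instead. Separate coefficients at T2 and T3 are an optional refinement with a further small gain.

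The cost is a sentence in Section 4 and a few terms in the model statement, with no new data. Statistically, it uses about one degree of freedom per added term and assumes linearity, which keeping the categories guards against. The form should be fixed before outcome data are examined, so that it cannot be said to have been chosen on the results.

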## 6.2 Appendix B

### Stata code for simulation of power

```
/* Program to simulate data */
program powersimu, rclass
    version 16.0
    syntax, b1(real) [alpha(real 0.05)]

    clear
    set obs 192
    gen id = _n in 1/192

    *correlation matrix; estimates from PHQ-9 data from LIFT1 trial
    matrix V = (27.95, 9.67, 3.91 \ ///
                 9.67, 19.28, 11.54 \ ///
                 3.91, 11.54, 11.78)
    matrix list V
    matrix M = (0 \ 0 \ 0)

    *random effect drawn from a multivariate normal distribution
    drawnorm e1 e2 e3, means(M) cov(V)

    *check that the covariances line up with expected
    correlate e1-e3, covariance

    *set the 8 different intervention versions
    gen condition=1 in 1/24
    replace condition=2 in 25/48
    replace condition=3 in 49/72
    replace condition=4 in 73/96
    replace condition=5 in 97/120
    replace condition=6 in 121/144
    replace condition=7 in 145/168
    replace condition=8 in 169/192

    *set up the effect coded intervention components
    gen dose=1 if inlist(condition,1,2,3,4)
    replace dose=-1 if inlist(condition,5,6,7,8)

    gen symptoms = 1 if inlist(condition,1,2,5,6)
    replace symptoms = -1 if inlist(condition,3,4,7,8)

    gen call = 1 if inlist(condition,1,3,5,7)
    replace call = -1 if inlist(condition,2,4,6,8)

    *reshape to long format for fitting the statistical model
    reshape long e, i(id) j(time)

    *dummy code time
    replace time = time-1
    gen time1 = 1 if time == 1
    gen time2 = 1 if time == 2
    replace time1 = 0 if time1 != 1
    replace time2 = 0 if time2 != 1

    *rename variables for easier coding
    rename (dose symptoms call) (d s c)
    *note that t2 is the primary time point
    rename (time1 time2) (t2 t3)

    *generate interactions ahead of time
    gen ds = d*s
    gen dc = d*c
    gen sc = s*c
    gen dsc = d*s*c

    foreach x in t2 t3 {
        gen d`x' = d*x'
        gen s`x' = s*x'
        gen c`x' = c*x'
        gen ds`x' = d*s*x'
        gen dc`x' = d*c*x'
        gen sc`x' = s*c*x'
        gen dsc`x' = d*s*c*x'
    }

    *generate PHQ-9 with a main effect on dose at t2. All other effects are null.
    gen phq9 = 13+`b1'*dt2+0*st2+0*ct2+0*dct2+0*sct2+0*dsct2+0*dt3+0*st3+0*ct3+0*dst3+ ///
```

```

0*dct3+0*sct3+0*dsct3+e

*run mixed model with unstructured covariance on the residuals
mixed phq9 t2 t3 dt2 st2 ct2 dst2 dct2 sct2 dsct2 dt3 st3 ct3 dst3 dct3 sct3 dsct3 ///

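### The primary model gives each minimisation variable a single effect shared by T1, T2 and T3; if these effects change over time, some precision at T2 is given away, and adding time products is a cheap improvement.

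*SAP*

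**What the plan says.** SAP section 2.4 states that "treatment assignment is conducted via a dynamic allocation minimization method", balancing on site, ICU type, T1 PHQ-9 stratum, T1 PHQ-10 stratum and age. Section 4 specifies a constrained longitudinal model with T1, T2 and T3 PHQ-9 as outcomes. It gives time interactions to the intervention components and then lists, as plain fixed effects, "and the variables used in the minimization allocation algorithm". The displayed equation has no covariates; the text after it adds "Note also that in practice we will adjust for the variables upon which the allocation was minimized", with the exception that "when PHQ-9 is the outcome, we will not adjust for baseline PHQ-9" and a matching exception for PHQ-10.

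Appendix A is consistent with this. Every component term is multiplied by `t2` or `t3`, while the covariates appear only as "mz_icu mz_age /*mz_phq9*/ mz_phq10 mz_site / solution". The residual covariance is unstructured: "REPEATED time / TYPE=un SUBJECT=recordid R RCORR". Neither document adds covariate-by-time terms or says why they are not needed.

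**The concern.** Because T1 is one of the outcomes, a covariate without a time product has one coefficient for all three visits. Where its true effects differ, the fitted value is a compromise. Part of the covariate's T2 effect then stays in the residual, and the T1 residual that the model uses to predict T2 is distorted.

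The T1 PHQ-10 stratum is the likeliest case. PHQ-10 is collected in the same T1 survey as the first PHQ-9 (Protocol section 7, Study Visits), so its association may well be strongest at T1 and fade.

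What is at stake is precision. Minimisation pays off in the reported SE only if the balancing variables are modelled adequately at the primary time point. One of the SAP's two routes for selecting a component is p < 0.05, so the SE enters the decision.

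**Working it through.** **Inputs from the SAP.** Covariance matrix (Appendix B): Var(T1) = 27.95, Var(T2) = 19.28, Var(T3) = 11.78, Cov(T1,T2) = 9.67, Cov(T1,T3) = 3.91, Cov(T2,T3) = 11.54. Analysed N = 192, from 240 with 20% dropout. Benchmark 1.6 points; two-sided alpha 0.05.

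**1. The plan's own figure.** In large samples the constrained model estimates a T2 effect with the T2 variance given T1:
- 19.28 − 9.67²/27.95 = 15.93
- SE = √(15.93 × 4/192) = 0.576
- Power at 1.6 points = Φ(1.6/0.576 − 1.96) = 79.3%

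Table 2 states 79.8%. The figure is reproduced, and its simulation has no covariates.

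**2. Is a constant PHQ-10 effect plausible?** The slope of T2 on T1 PHQ-9 is 9.67/27.95 = 0.35, and of T3 on T1 is 3.91/27.95 = 0.14. A 5-point contrast at T1 (assumed) that acts only through T1 would be 1.73 points at T2 and 0.70 at T3. The SD falls from 5.29 to 4.39 to 3.43, so an effect constant in points would need the T1 stratum's correlation with PHQ-9 to rise by a factor of 5.29/3.43 = 1.54 by T3. That is unlikely, though no document rules it out.

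**3. Large-sample cost in that case.** Take a binary covariate with 50% prevalence (assumed) and effects d = (5, 1.73, 0.70), holding total covariance at the SAP matrix V.
- With time products the residual covariance is V − 0.25dd′. Its entries are 21.70 (T1), 7.51 (T1,T2) and 18.53 (T2). Conditional variance = 18.53 − 7.51²/21.70 = 15.93; SE 0.576.
- As coded, generalised least squares gives a common coefficient b = 2.02, and the misfit 0.25(d − b)(d − b)′ is added back. The entries become 23.93, 7.29 and 18.55. Conditional variance = 18.55 − 7.29²/23.93 = 16.33; SE 0.583.

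The coded model is therefore about 1.2% less precise than either the by-time model or no adjustment.

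**4. Simulation at trial size.** 800 trials per scenario, 240 patients allocated by minimisation (probability 0.8, assumed), 20% dropout after T1, REML with unstructured covariance. Covariate effects and prevalences are assumptions. Power is as coded, then by time.

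| Assumed PHQ-10 effect at T1/T2/T3 | SE, no covariates | SE, as coded | SE, by time | Power at 1.6 |
|---|---|---|---|---|
| none | 0.5761 | 0.5767 | 0.5788 | 79.4%, 78.1% |
| 2/2/2 | 0.5760 | 0.5685 | 0.5704 | 77.6%, 76.7% |
| 5/2.5/1 | 0.5747 | 0.5744 | 0.5736 | 80.0%, 81.0% |
| 6/2.08/0.84 | 0.5763 | 0.5931 | 0.5791 | 77.7%, 78.5% |
| 5/1/0 | 0.5750 | 0.5907 | 0.5744 | 76.0%, 79.4% |
| 4/4/2 plus age and site effects | 0.5785 | 0.5423 | 0.5390 | 83.8%, 84.4% |
| 5/2.5/1 plus other time-varying effects | 0.5766 | 0.5805 | 0.5557 | 80.1%, 83.1% |
| 0/3/1 | 0.5799 | 0.5730 | 0.5386 | 80.4%, 84.3% |

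Moving from the coded to the by-time model changes the SE by +0.4% (0.5788/0.5767) at worst and −6.0% (0.5386/0.5730) at best. Simulation error is about 1.4 points on each power figure.

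**5. Validity.** Under the coded model the mean error was at most 0.03 points and type I error was 3.6% to 6.0%, within simulation error of 5%. The observed scatter of the estimates differed less between the two models than the reported SEs did: as coded relative to by time, from −0.5% (0.5843 against 0.5870, no effect) to +2.0% (0.5592 against 0.5484, several effects). Most of the loss is thus a reported SE wider than the balanced allocation warrants.

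**The case against.** A common covariate effect is a legitimate and parsimonious specification, the SAP calls the code an example, and no document shows that any covariate effect changes over time. Because the unstructured covariance already links T2 to T1, many fading patterns cost nothing visible, such as 5/2.5/1 above. The largest loss needs an effect absent at T1 and strong at T2, for which the documents offer no support. The case where adjustment does worse than none needs a T1 effect of about 5 points, nearly one baseline SD of 5.3; there the time products only restore the unadjusted precision. The effect on decisions is also small: the 1.6-unit route ignores the SE, and on the p-value route a 6% larger SE raises the estimate needed from 1.96 × 0.576 = 1.13 to about 1.20 points.

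All of this stands, and it makes the point optional. It does not remove it, because the constant-effect assumption is nowhere argued, it is unlikely for the PHQ-10 stratum, and relaxing it costs at most about 0.4% in SE in these scenarios.

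A reader might infer that T2 is adjusted with a wrong coefficient and that the standard errors are certainly too wide. The documents do not support that: both depend on unknown covariate effects, and with constant effects the coded model is right and marginally more efficient. Nor do they support an inference that the component estimates are biased, or that the stated power is wrong.

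**Conclusion.** The structure is as described, in both the SAP text and the code. It is an efficiency weakness of modest and uncertain size: under the assumed effects, time products change the SE of a T2 main effect by between 0.4% worse and about 6% better, with up to about 3 to 4 points of power at 1.6 points. These sizes rest on assumed covariate effects, prevalences and minimisation probability, with the total covariance held at the SAP matrix. The change is worth making because it is cheap; the primary analysis remains valid without it.

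**What to change.** In Appendix A, add the products of `t2` and `t3` with `mz_icu`, `mz_age`, `mz_phq10` and `mz_site`, and add a sentence to SAP section 4 saying that the minimisation variables have time-specific effects. Use the same form for the secondary outcomes, keeping the section 4 exceptions: omit `mz_phq9` and its products when PHQ-9 is the outcome, and `mz_phq10` and its products when PHQ-10 is the outcome. For other outcomes both strata enter with their products. If the team prefers the common-effect form, it should state and justify the constant-effect assumption.

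The cost for PHQ-9 is 12 parameters: ICU type (2), age (1), PHQ-10 (1) and site (2), at two follow-up times. The existing component estimate statements do not change. The plain `t2` and `t3` coefficients would then refer to the covariates' reference categories, so estimated means per condition should be averaged over the covariates. The SE penalty is negligible if effects are truly constant.
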